- 6) Presence of type 0 fibroids, unless < 1 cm in diameter and are unlikely to contribute to bleeding in the judgment of the investigator.
- 7) Presence of a single polyp ≥ 1.5 cm, or multiple polyps of any size, within the uterine cavity, or excision of polyps within three months of completing any screening procedures
- 8) Any fibroid of FIGO type 1, type 2, type 3, type 4, or type 2-5 with diameter > 5.0 cm as determined by transvaginal sonography or magnetic resonance imaging (MRI)
- 9) Bulk symptoms (pelvic pressure, frequent urination) that significantly interfere with normal daily activities in the presence of one or more fibroids of FIGO type 5, type 6, or type 7
- 10) Exclusive presence of fibroids that, despite meeting other eligibility criteria, are insufficient to explain the severity of symptoms in the judgment of the Investigator
- 11) Presence of clinically relevant fibroids that cannot be treated for technical reasons (e.g. cervical fibroid)
- 12) Presence of an extrauterine pelvic mass that has not been diagnosed as benign
- 13) IUD/IUS in situ within the washout period specified in Appendix H prior to undergoing any screening procedures
- 14) Not used
- 15) Previous procedure for fibroids or heavy menstrual bleeding other than myomectomy. Examples of excluded procedures: endometrial ablation,

- uterine artery/fibroid embolization, uterine artery occlusion, MR guided focused ultrasound, radiofrequency ablation.
- 16) Myomectomy by any route within 12 months prior to undergoing any screening procedures, or myomectomy > 12 months with less than 6 months of symptom relief
 - 17) Any abnormality of the endometrial cavity that, in the judgment of the Investigator, obstructs access of the Sonata Handpiece to the endometrial cavity or fibroids (e.g., significant intrauterine synechiae)
 - 18) Contraindication to MRI, including MR-incompatible implants, allergy to contrast media or claustrophobia, and weight that is above the limitation of the site-specific MRI scanner credentialed for the study
 - 19) Total uterine volume \geq 1000 cc as determined by transvaginal sonography
 - 20) Clinically significant adenomyosis based on sonography; presence confirmed by MRI (defined as more than 10% of the junctional zone measuring more than 10 mm in thickness as measured by MRI)
 - 21) Confirmed or suspected diagnosis of clinically relevant endometriosis

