9.1 CO-PRIMARY ENDPOINTS & SUCCESS CRITERIA

Table 1 provides a list of the test method, subject success criteria, and study success criteria for the co-primary endpoints. The co-primary endpoints are reached at 12 months.

Table 1 Co-Primary Endpoints & Success Criteria

Co-Primary Endpoint	Test Method	Subject Success Criteria ^{Note 1}	Study Success Criteria ^{Note 2}
Reduction in Menstrual Blood Loss (MBL) at 12 months	Pictorial blood loss assessment chart (PBAC), Appendix F. This is a validated measure of MBL ⁹ . Scoring instructions are included in Appendix G.	≥ 50% reduction in PBAC score, and a final PBAC score < 250	LCL of the percentage of subject success ≥ 45%
Rate of surgical re-intervention for HMB due to treatment failure at 12 months	Surgical re-intervention for HMB due to treatment failure	No surgical re-intervention for HMB due to treatment failure at 12 months	LCL of the percentage of subject success ≥ 75%

Table Notes

- 1) Subject success is calculated separately for the two co-primary endpoints, such that it is possible for a subject to be considered a success for one co-primary endpoint and not for the other.
- 2) Study success is achieved if both of the study success criteria are met.

⁹ Janssen C, Scholten P, Heintz P. A simple visual assessment technique to discriminate between menorrhagia and normal menstrual blood loss. *Obstet & Gynec.* 1995;85:977-982.

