Moderate	Surgery lasting less than 30 minutes in patients with additional risk factors; surgery lasting less than 30 minutes in patients aged 40–60 years with no additional risk factors; major surgery in patients younger than 40 years with no additional risk factors	Low-dose unfractionated heparin (5,000 units every 12 hours), low molecular weight heparin (2,500 units dalteparin or 40 mg enoxaparin daily), graduated compression stockings, or intermittent pneumatic compression device
High	Surgery lasting less than 30 minutes in patients older than 60 years or with additional risk factors; major surgery in patients older than 40 years or with additional risk factors	Low-dose unfractionated heparin (5,000 units every 8 hours), low molecular weight heparin (5,000 units dalteparin or 40 mg enoxaparin daily), or intermittent pneumatic compression device
Highest	Major surgery in patients older than 60 years plus prior venous thromboembolism, cancer, or molecular hypercoagulable state	Low-dose unfractionated heparin (5,000 units every 8 hours), low molecular weight heparin (5,000 units dalteparin or 40 mg enoxaparin daily), or intermittent pneumatic compression device/graduated compression stockings + low-dose unfractionated heparin or low molecular weight heparin Consider continuing prophylaxis for 2–4 weeks after discharge.

Modified from Geerts WH, Pineo GF, Helt JA, Bergqvist D, Lassen MR, Colwell CW, et al. Prevention of venous thromboembolism: the Seventh ACCP Conference on Antithrombotic and Thrombolytic Therapy. Chest 2004;126(suppl):338S–400S.

E. Sonata Treatment

- 1) The treatment shall be performed in accordance with the physician Instructions for Use. Highlights are provided below.
 - (a) The intent is for all clinically relevant fibroids to be ablated during a single treatment session.
 - (b) Coincidental removal of an intrauterine polyp up to a maximum diameter of 1.5 cm and type 0 fibroids < 1.0 cm is allowed.
 - (c) A small number of sponsor representatives (generally one to three individuals) may be present during the procedure to provide equipment support if needed as well as for proctoring and general observation.
- 2) **Treatment and Recovery Assessments**
The following data will be collected on the day of the treatment prior to discharge:
 - (a) Treatment location (e.g. ambulatory care center, operating room, etc.)

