Access to the investigational devices shall be controlled and the investigational devices shall be used only in the clinical investigation with Sponsor approval and according to the protocol. The Investigator or an authorized designee shall maintain adequate records documenting the receipt, use, return, and disposal of all investigational devices, which shall include,

- A. The date of receipt
- B. Identification of each investigational device (batch number, lot/serial number or unique code),
- C. The expiry date, if applicable,
- D. The date(s) of use,
- E. Identification of the subject on whom the device was used,
- F. The date of return of unused, expired or malfunctioning investigational devices.

When the enrollment is complete, the Investigator shall return to the study sponsor any unused devices and a copy of the completed device inventory.

19 **STATISTICAL CONSIDERATIONS**

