5.5.1.2 Surgical Reintervention

Subjects will be asked to indicate whether there has been any surgical reintervention for the treatment of HMB since their last visit. The rate of surgical reintervention for HMB due to treatment failure will be evaluated throughout all assessment timepoints and at 12 months as a co-primary endpoint. Surgical reintervention for the treatment of HMB includes the following procedures:

- a) Hysterectomy (abdominal, vaginal, laparoscopic)
- b) Myomectomy (abdominal, vaginal, laparoscopic, hysteroscopic)
- c) Uterine artery embolization
- d) Magnetic resonance-guided focused ultrasound (MRgFUS) or similar focused ultrasound treatment
- e) Endometrial ablation (nonresectoscopic, hysteroscopic)

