5.6.8.2 Handling of Dropouts or Missing Data

Reduction in MBL at 12 Months

Missing 12-month menstrual blood loss data will be imputed using last observation carried forward (LOCF). Subjects which undergo surgical reintervention to manage fibroid symptoms prior to 12 months will be excluded from the Reduction in Menstrual Blood Loss analysis.

Surgical Reintervention for HMB due to Treatment Failure at 12 Months

Life-Table methods will be used to calculate the success rate and 95% confidence interval for the rate of surgical reintervention during 12 months. Therefore, subjects that are discontinued prior to 12 months for reasons other than surgical reintervention will be considered censored.

Sensitivity Analyses

Sensitivity analyses will also be conducted to examine the impact of missing data. A worst-case analysis (all missing data imputed as failures) and best-case analysis (all missing data imputed as successes) will be performed. In addition, a tipping point analysis will be performed.

Secondary Endpoint Analyses

No imputations will be made for missing secondary endpoint data.

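### Does the list of procedures counted as surgical reintervention leave out events that the co-primary endpoint should count?

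*SAP*

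**What the plan says.** - **Event definition.** SAP 5.5.1.2 has women asked about every surgical reintervention for heavy menstrual bleeding (HMB) since the previous visit. It then says "Surgical reintervention for the treatment of HMB includes the following procedures" and gives five items. Only item (d) carries its own extension: "Magnetic resonance-guided focused ultrasound (MRgFUS) or similar focused ultrasound treatment".
- **Success criterion.** Protocol Table 1 gives no list: "No surgical re-intervention for HMB due to treatment failure at 12 months". The study criterion is a lower 95% limit of at least 75%.
- **Procedures named elsewhere.** Protocol Section 4L, exclusion criterion 15, gives as examples of excluded earlier procedures "uterine artery/fibroid embolization, uterine artery occlusion, MR guided focused ultrasound, radiofrequency ablation".
- **Analysis.** SAP 5.6.8.2 uses a life table in which "subjects that are discontinued prior to 12 months for reasons other than surgical reintervention will be considered censored". For menstrual blood loss (MBL), women with "surgical reintervention to manage fibroid symptoms prior to 12 months will be excluded from the Reduction in Menstrual Blood Loss analysis".
- **Collection.** Protocol 12.3 asks at 30 days, 3, 6 and 12 months and 2 and 3 years whether the woman has had any surgery for heavy bleeding, and records the procedure and its date. Protocol Table 4 and SAP Table 2 mark the item only at 6 and 12 months and 2 and 3 years.

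**The concern.** This is the event definition of a co-primary endpoint in a single-arm trial with a fixed threshold. The SAP list is the only one in the two documents. It omits two procedures that the protocol itself treats as fibroid or HMB treatments, one of them the same type of treatment as the study device. Because item (d) has its own extension and the other items have none, a reader could take the list as closed. A woman retreated by an unlisted procedure would then be event-free, or censored if she left the study.

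The schedule tables seem to add a second leak. If the forms followed the tables, and the month-6 question reached back only to the 3-month visit, a reintervention in the first three months could go unasked. Within this endpoint, an uncounted event can only raise the reintervention-free rate.

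**Working it through.** **1. The plan's own figure.** SAP Table 4 and Protocol 19.1 B give N = 75 for a 75% threshold, an assumed 90% rate and 90% power. With the exact two-sided 95% limit, 64/75 gives a lower limit of 0.7527 (pass) and 63/75 gives 0.7372 (fail). Power is P(X ≥ 64 | n = 75, p = 0.90) = 0.931, and the one-sided error at p = 0.75 is 0.022. The figure reproduces, and the procedure list does not enter it.

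**2. Open or closed list?**

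| Text | Reading it supports |
|---|---|
| SAP 5.5.1.2, verb introducing the list | open |
| SAP 5.5.1.2, first sentence, covers every surgical reintervention for HMB | open |
| Protocol Table 1, criterion without a list | open |
| Protocol 12.3, asks about any procedure and records type and date | open |
| SAP 5.5.1.2 item (d), its own extension | closed, by inference only |
| Protocol exclusion 15 | neither; it governs eligibility |

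A closed list would also make the SAP narrower than the protocol endpoint that it implements. Repeat treatment with the study device is unlikely in any case: "The intent is for all clinically relevant fibroids to be ablated during a single treatment session", and Protocol Section 18 requires that "the investigational devices shall be used only in the clinical investigation with Sponsor approval and according to the protocol".

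**3. What must fail for an early event to be missed.** All of these together:

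- Sites follow the tables and ignore the visit text for 30 days and 3 months.
- The SAP's look-back to the previous visit replaces the protocol question at 6 and 12 months, which has no look-back limit.
- The update of medical history and symptoms, which both tables do mark at 10 days, 30 days and 3 months, fails to reveal the operation.
- If she withdraws early, the exit assessment also misses it. Protocol 10.6 C asks for as many month-12 procedures as possible, and the tables mark reintervention at month 12.

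**4. Events the criterion tolerates.** Inputs: n = 147 and 15% dropout, about 22 women (Protocol 19.1 C). Assumptions: intervals 0–1, 1–3, 3–6 and 6–12 months, events and dropouts spread evenly, log-log interval (the SAP names none). For each interval n′ = number at risk − dropouts/2 and q = events/n′. Then S = Π(1 − q), g = Σ q/[n′(1 − q)], and LCL = S^exp(1.96√g/|ln S|).

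With 23 events:

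| Interval (months) | At risk | n′ | Events | S |
|---|---|---|---|---|
| 0–1 | 147 | 146.08 | 1.92 | 0.9869 |
| 1–3 | 143.25 | 141.42 | 3.83 | 0.9601 |
| 3–6 | 135.75 | 133.00 | 5.75 | 0.9186 |
| 6–12 | 124.50 | 119.00 | 11.50 | 0.8298 |

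The standard error S√g is 0.0324, so √g = 0.0324/0.8298 = 0.0390, and |ln S| = 0.1866. The exponent is exp(1.96 × 0.0390/0.1866) = 1.507, and LCL = 0.8298^1.507 = 0.755: pass. With 24 events S = 0.8224 and LCL = 0.747: fail. With 20% dropout (SAP 5.6.7, 29 women), 22 events pass (0.756) and 23 fail (0.748). With no censoring and the exact limit, 26 events pass (121/147, 0.7517) and 27 fail (120/147, 0.7441).

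At the planned 90% rate about 13.6 events are expected, so the margin is 23 − 13.6, or about 9 events.

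**5. Chance of passing if some events go uncounted.** Simulated with constant hazard and 15% dropout. The documents give no frequency for such retreatments, so the uncounted shares are assumptions.

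| True rate | 0% | 5% | 10% | 20% |
|---|---|---|---|---|
| 90% | 99.6% | 99.8% | 99.9% | 100.0% |
| 85% | 79% | 86% | 91% | 97% |
| 80% | 23% | 34% | 45% | 69% |
| 75% | 2.0% | 4.1% | 8.0% | 24% |

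Uncounted women are treated here as event-free to 12 months. If they are censored at the procedure, the 20% column falls from 24% to 19% at a true 75%.

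**6. The other co-primary.** A woman counted as a reintervention leaves the MBL analysis. As an arithmetic illustration, 75/125 = 60.0% becomes 75/122 = 61.5% if three MBL failures leave. If instead she stays in with a diary score lowered by the second procedure, she may score as an MBL success. So counting more retreatments lowers one co-primary rate and can move the other either way. The net direction for study success, which needs both, is not fixed.

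**The case for a change.** The strongest case for a change is that the edit is cheap and that an event rule should be settled before anyone sees data. If the sponsor already means an open list and questions at 30 days and 3 months, new wording only records that. If not, it closes a route that flatters a co-primary. The adverse-event form is not a dependable backstop either, because Protocol 14.1 A, note 3, says an elective reintervention for HMB is not an adverse event.

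Parts of this stand. The two procedures are unnamed, the tables do disagree with Protocol 12.3, and the lower rows of the last table above show that a 20% loss of events would matter if the true rate were 75–80%. But that share has no basis in the documents, and the loss itself needs the weaker reading of the list or a chain of collection failures.

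The obvious edits also have a price. A catch-all item would raise new questions about which minor procedures count. Tying the MBL exclusion to the same list would attach a rule about fibroid symptoms in general to a list confined to HMB, and could change who is in that analysis.

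**Conclusion.** No change follows. The list is a gap that analysts can fill from the documents as they stand: a surgical procedure for HMB due to treatment failure is an event whether or not it is named, and its type and date are recorded. The month-6 start in the two tables is a clerical slip; the visit text in Protocol 12.3 states the intended collection and should be followed.

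No sample size or power figure is affected. At the planned 90% rate the criterion has room for about 9 events beyond the 13.6 expected, and the chance of passing is at least 99.6% throughout the range examined. This rests on three assumptions: sites work from Protocol 12.3, the case report forms (not among the documents) carry its question, and the true rate is not close to 75%.

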5.5.2 Secondary Efficacy Variables

5.5.2.1 Total and Perfused Fibroid Volumes

Total and perfused fibroid volumes will be evaluated at baseline and at 12 months using contrast-enhanced MRI. The MRI's will be evaluated by a central reader.

5.5.2.2 Uterine Fibroid Symptom and Quality of Life (UFS-QOL)

The UFS-QOL is detailed in Appendix A. The Symptom Severity Score (SSS) and Health-Related Quality of Life Score (HRQL) are calculated from a subset of the UFS-QOL questionnaire. UFS-QOL scoring instructions are detailed in Appendix B.

5.5.2.3 Overall Treatment Effect (OTE)

Subjects will be asked to indicate whether their uterine fibroid symptoms have improved, remained the same, or worsened. If the subject indicates that her symptoms have improved, she will be asked to rate the degree of improvement on a 7-point scale from “almost the same, hardly

better at all” (1) to “a very great deal better” (7). If the subject indicates that her symptoms worsened, she will be asked to rate the degree of worsening on a 7- point scale from “almost the same, hardly worse at all” (-1) to “A very great deal worse” (-7).

5.5.2.4 Subject Satisfaction

Subjects will be asked to rate their satisfaction with the treatment, with responses based on a 6-point Likert scale ranging from “very satisfied” to “very dissatisfied”. They will also be asked if they would recommend the treatment to a friend with the same health problems using a 4-point scale from “definitely yes” to “definitely not”.

5.5.2.5 EuroQOL EQ-5D

The EQ-5D should be completed during the subject’s 3rd, 6th, and 12th menstrual cycles post-treatment, preferably on the first full day of bleeding. It should again be completed at 2 years and at 3 years post-treatment. It should be completed based solely on symptoms from that cycle. If the subject has become amenorrheic, the EQ-5D may be completed at any time during the follow-up visit window.

5.5.3 Procedure Variables

Procedure information will be captured within the eCRF. The device insertion and removal times will be collected to facilitate the calculation of procedure time. Additionally, the time the subject entered the procedure room, exits the procedure room, was eligible for discharge, and was actually discharged will be collected. The procedure location will be captured (e.g. ambulatory care center, operating room, etc). The anesthesia and procedure-related medications, and number and size of each fibroid treated will also be captured, along with the number of ablations for each fibroid. In addition, an eCRF will be created to capture device malfunctions.

5.5.3.1 Subject Pain and Tolerance of Procedure

Prior to discharge, subjects will be asked to rate their tolerance of the procedure and rate their experience of pain using a pain visual analog scale.

5.5.3.2 Treatment Recovery Questionnaire

Subjects will be given a Treatment Recovery Questionnaire at discharge and asked to complete questions daily regarding return to normal activities for the first two weeks post-procedure. A copy of the questionnaire is included as Appendix C.

5.5.3.3 Length of Stay (LOS)

The length of stay, in hours, will be assessed by recording the duration of the institutional stay from the start of procedure to discharge (time of insertion of device to time of discharge). If

recovery time is not longer than expected and study center scheduling prevents same-day discharge, LOS will be calculated based on the time at which discharge would otherwise have occurred as documented by the Investigator in the CRF.

5.5.4 Safety Variables

5.5.4.1 Adverse Events

Adverse events will be reported and classified by the Investigator using the specific medical diagnosis, or using signs, symptoms or abnormal laboratory values if no medical diagnosis can be identified.

5.5.4.2 Adverse Event Definitions

A. Adverse Event (AE) - Any untoward medical occurrence, unintended disease or injury or any untoward clinical signs (including an abnormal laboratory finding) in subjects, users or other persons whether or not related to the investigational medical device.

NOTE 1: This includes events related to the procedures involved.

NOTE 2: For users or other persons this is restricted to events related to the investigational medical device.

NOTE 3: An elective surgical reintervention for HMB or change in a endpoint is not considered an adverse event.

NOTE 4: An overnight stay for observation does not constitute hospitalization for the purposes of this protocol as long as there are no reported adverse events associated with the stay.

B. Adverse Device Effect (ADE) – Adverse Event related to the use of a medical device. This includes:

- 1) Any adverse event resulting from insufficiencies or inadequacies in the instructions for use, the deployment, the installation, the operation, or any malfunction of the medical device.
- 2) Any event that is a result of a use error or intentional misuse.

C. Serious Adverse Event (SAE) - Adverse Event that

- 1) Led to death
- 2) Led to a serious deterioration in the health of the subject that either:
 - a) resulted in a life-threatening illness or injury, or
 - b) resulted in a permanent impairment of a body structure or a body function, or

- c) required in-patient hospitalization or prolongation of existing hospitalization, of more than 24 hours, or
 - d) resulted in medical or surgical intervention to prevent life threatening illness or injury or permanent impairment to a body structure or a body function.
- 3) Led to fetal distress, fetal death or congenital abnormality or birth defect

NOTE 1: A planned hospitalization for a pre-existing condition, or a procedure required by the clinical investigational plan, without a serious deterioration in health, is not considered to be a serious adverse event.

NOTE 2: If recovery time from treatment with the VizAblate System is not longer than expected and site scheduling prevents same-day discharge, overnight stay is not considered prolonged hospitalization for purposes of classification as an SAE.

D. Serious Adverse Device Effect (SADE) – Adverse device effect that has resulted in any of the consequences characteristic of a serious adverse event.

E. Unanticipated Adverse Device Effect (UADE) - Serious adverse device effect which by its nature, incidence, severity or outcome has not been identified in the current version of the risk analysis as presented in the Investigator's Brochure.

